### 3.1.2 IRB Approval

Each investigator or group of investigators at a clinical site must obtain IRB approval for this protocol and submit IRB approval and supporting documentation to the CTSU Regulatory Office before they can be approved to enroll patients. For CTEP and Division of Cancer Prevention (DCP) studies open to the National Clinical Trials Network (NCTN) and NCI Community Oncology Research Program (NCORP) Research Bases after March 1, 2019, all U.S.-based sites must be members of the NCI Central Institutional Review Board (NCI CIRB). In addition, U.S.-based sites must accept the NCI CIRB review to activate new studies at the site after March 1, 2019. Local IRB review will continue to be accepted for studies that are not reviewed by the CIRB, or if the study was previously open at the site under the local IRB. International sites should continue to submit Research Ethics Board (REB) approval to the CTSU Regulatory Office following country-specific regulations.

Sites participating with the NCI CIRB must submit the Study Specific Worksheet for Local Context (SSW) to the CIRB using IRBManager to indicate their intent to open the study locally. The NCI CIRB's approval of the SSW is automatically communicated to the CTSU Regulatory Office, but sites are required to contact the CTSU Regulatory Office at [[contact]](mailto:[contact]) to establish site preferences for applying NCI CIRB approvals across their Signatory Network. Site preferences can be set at the network or protocol level. Questions about establishing site preferences can be addressed to the CTSU Regulatory Office by email or calling [name].

Sites using their local IRB or REB, must submit their approval to the CTSU Regulatory Office using the Regulatory Submission Portal located in the Regulatory section of the CTSU website. Acceptable documentation of local IRB/REB approval includes:

- Local IRB documentation;
- IRB-signed CTSU IRB Certification Form; and/or
- Protocol of Human Subjects Assurance Identification/IRB Certification/Declaration of Exemption Form.

In addition, the Site-Protocol Principal Investigator (PI) (i.e. the investigator on the IRB/REB approval) must meet the following criteria in order for the processing of the IRB/REB approval record to be completed:

- Holds an active CTEP status;
- Rostered at the site on the IRB/REB approval (*applies to US and Canadian sites only*) and on at least one participating roster;
- If using NCI CIRB, rostered on the NCI CIRB Signatory record;
- Includes the IRB number of the IRB providing approval in the Form FDA 1572 in the RCR profile; and
- Holds the appropriate CTEP registration type for the protocol.

### Additional Requirements

Additional requirements to obtain an approved site registration status include:

- An active Federal Wide Assurance (FWA) number;
- An active roster affiliation with the Lead Protocol Organization (LPO) or a Participating Organization (PO); and
- Compliance with all protocol-specific requirements (PSRs).

For information about the submission of IRB/REB approval documents and other regulatory documents as well as checking the status of study center registration packets, please see [Appendix X](#).

Institutions with patients waiting that are unable to use the Portal should alert the CTSU Regulatory Office immediately at [name] in order to receive further instruction and support. For general (non-regulatory) questions call the CTSU General Helpdesk at: [name].

**Note: Sites participating on the NCI CIRB initiative and accepting CIRB approval for the study are not required to submit separate IRB approval documentation to the CTSU Regulatory Office for initial, continuing or amendment review.**

Investigators and site staff will need to be registered with CTEP and have a valid and active Cancer Therapy Evaluation Program-Identity and Access Management (CTEP-IAM) account (check at <<https://ctepcore.nci.nih.gov/iam/>>). This is the same account (user id and password) used for credentialing in the CTSU members' web site. To perform registrations in OPEN, the site user must have been assigned the 'Registrar' role on the relevant Group or CTSU roster. OPEN can be accessed at <https://open.ctsu.org> or from the OPEN tab on the CTSU members' side of the website at <https://www.ctsu.org>. Registrars must hold a minimum of an AP registration type.

### 3.1.3 Genetic Screening Procedures for Eligibility

Patient enrollment onto the APEC1621SC screening protocol is required. In Stage 2 of Pediatric MATCH (effective with Amendment #4 of APEC1621SC for patients enrolling on screening protocol) tumor genomic testing results from a CAP/CLIA-certified laboratory will be reviewed by the APEC1621SC Molecular Review Committee after APEC1621SC screening protocol enrollment to confirm the identification of an actionable Mutation of Interest (aMOI) for which a MATCH treatment subprotocol is available. Questions regarding interpretation of tumor testing results for potential APEC1621A study patients (such as whether a specific mutation would be considered actionable for the study) should be directed to the APEC1621SC and APEC1621A study chairs.

The treatment assignment to a MATCH to a subprotocol (if a relevant aMOI is detected) will be communicated to the enrolling institution via the COG treatment assignment mechanism, upon which a reservation to APEC1621A will be secured by COG. Reservations should be withdrawn by the institution if at any point the patient indicates they do NOT intend to consent to participation or the site investigator indicates the patient will never be eligible for APEC1621A.

### 3.2 Informed Consent/Assent

The investigational nature and objectives of the trial, the procedures and treatments involved and their attendant risks and discomforts, and potential alternative therapies will be carefully explained to the patient or the patient's parents or guardian if the patient is a child, and a signed informed consent and assent will be obtained according to institutional guidelines.

### 3.3 Screening Procedures

Diagnostic or laboratory studies performed exclusively to determine eligibility for this trial must only be done after obtaining written informed consent. This can be accomplished through the study-specific protocol. Documentation of the informed consent for screening will be maintained in the patient's research chart. Studies or procedures that were performed for clinical indications (not exclusively to determine eligibility) may be used for baseline values even if the studies were done before informed consent was obtained.

### 3.4 Eligibility Checklist

Before the patient can be enrolled, the responsible institutional investigator must sign and date the completed eligibility checklist. A signed copy of the checklist will be uploaded into RAVE immediately following enrollment.

### 3.5 Study Enrollment

Following a MATCH treatment assignment to a protocol, patients may be enrolled on the study once all eligibility requirements for the study have been met. Before enrolling a patient on study, the Study Chair or Vice Chair should be notified. Patients who give informed consent for the protocol in order to undergo screening for eligibility are not considered enrolled and should not be enrolled until the screening is completed and they are determined to meet all eligibility criteria. Study enrollment in Stage 2 of Pediatric MATCH (effective with Amendment #4 of APEC1621SC for patients enrolling on screening protocol) is outlined in [Section 3.1.3](#).

Patients must be enrolled within 2 weeks (14 days) of treatment assignment. The date protocol therapy is projected to start must be no later than seven (7) calendar days after the date of study enrollment. Patients enrolling onto APEC1621A will have a COG ID obtained through their prior enrollment onto the master screening protocol or from a prior COG study. Patients who are started on protocol therapy prior to study enrollment will be considered ineligible.

All clinical and laboratory studies to determine eligibility must be performed within 7 days prior to enrollment unless otherwise indicated in the eligibility section below.

**Note: No starter supplies will be provided. Drug orders of LOXO-101 (larotrectinib) should be placed with CTEP after enrollment and treatment assignment to APEC1621A with consideration for timing of processing and shipping to ensure receipt of drug supply prior to start of protocol therapy.**

### 3.6 Institutional Pathology Report

The institutional pathology report from the tumor specimen submitted for sequencing will have been uploaded into RAVE immediately following enrollment on the APEC1621SC screening protocol.

### 3.7 Dose Assignment

The dose level will be assigned via OPEN at the time of study enrollment.

## 4.0 PATIENT ELIGIBILITY

All clinical and laboratory studies to determine eligibility must be performed within 7 days prior to enrollment unless otherwise indicated. Laboratory values used to assess eligibility must be no older than seven (7) days at the start of therapy. Laboratory tests need **not** be repeated if therapy starts **within** seven (7) days of obtaining labs to assess eligibility. If a post-enrollment lab value is outside the limits of eligibility, or laboratory values are older than 7 days, then the following laboratory evaluations must be re-checked within 48 hours prior to initiating therapy: CBC with differential, bilirubin, ALT (SGPT) and serum creatinine. If the recheck is outside the limits of eligibility, the patient may not receive protocol therapy and will be considered off protocol therapy. Imaging studies, bone marrow biopsy and/or aspirate (when applicable) must be obtained within 14 days prior to start of protocol therapy (repeat the tumor imaging if necessary).

Clarification in timing when counting days: As an example, please note that if the patient's last day of prior therapy is September 1st, and the protocol requires waiting at least 7 days for that type of prior therapy, then that patient cannot be enrolled until September 8th.

**Important note:** The eligibility criteria listed below are interpreted literally and cannot be waived. All clinical and laboratory data required for determining eligibility of a patient enrolled on this trial must be available in the patient's medical or research record which will serve as the source document for verification at the time of audit.

### 4.1 Inclusion Criteria

4.1.1 APEC1621SC: Patient must have enrolled onto APEC1621SC and must have been given a treatment assignment to MATCH to APEC1621A based on the presence of an actionable mutation as defined in APEC1621SC. Examples of actionable mutations for APEC1621A are listed in [Appendix VIII](#).

4.1.2 Age: Patients must be  $\geq$  than 12 months and  $\leq$  21 years of age at the time of study enrollment.

4.1.3 Disease Status:

Patients must have radiographically **measurable** disease (see [Section 12](#)) at the time of study enrollment. Patients with neuroblastoma who do not have measurable disease but have MIBG+ evaluable disease are eligible. Measurable disease in patients with CNS involvement is defined as any lesion that is at minimum 10 mm in one dimension on standard MRI or CT.

Note: The following do not qualify as measurable disease:

- malignant fluid collections (e.g., ascites, pleural effusions)
- bone marrow infiltration except that detected by MIBG scan for neuroblastoma
- lesions only detected by nuclear medicine studies (e.g., bone, gallium or PET scans) except as noted for neuroblastoma
- elevated tumor markers in plasma or CSF
- previously radiated lesions that have not demonstrated clear progression post radiation

- leptomeningeal lesions that do not meet the measurement requirements for RECIST 1.1.

4.1.4 Performance Level: Karnofsky  $\geq 50\%$  for patients  $> 16$  years of age and Lansky  $\geq 50$  for patients  $\leq 16$  years of age (See [Appendix I](#)). Note: Neurologic deficits in patients with CNS tumors must have been relatively stable for at least 7 days prior to study enrollment. Patients who are unable to walk because of paralysis, but who are up in a wheelchair, will be considered ambulatory for the purpose of assessing the performance score.

4.1.5 Prior Therapy

4.1.5.1 Patients must have fully recovered from the acute toxic effects of all prior anti-cancer therapy and must meet the following minimum duration from prior anti-cancer directed therapy prior to enrollment. If after the required timeframe, the numerical eligibility criteria are met, e.g. blood count criteria, the patient is considered to have recovered adequately.

- a. Cytotoxic chemotherapy or other anti-cancer agents known to be myelosuppressive.  
See <https://www.cogmembers.org/site/disc/devtherapeutics/default.aspx> for commercial and Phase 1 investigational agent classifications. For agents not listed, the duration of this interval must be discussed with the study chair and the study-assigned Research Coordinator prior to enrollment.
  - i.  $\geq 21$  days after the last dose of cytotoxic or myelosuppressive chemotherapy (42 days if prior nitrosourea).
- b. Anti-cancer agents not known to be myelosuppressive (e.g. not associated with reduced platelet or ANC counts):  $\geq 7$  days after the last dose of agent.  
See <https://www.cogmembers.org/site/disc/devtherapeutics/default.aspx> for commercial and Phase 1 investigational agent classifications. For agents not listed, the duration of this interval must be discussed with the study chair and the study-assigned Research Coordinator prior to enrollment.
- c. Antibodies:  $\geq 21$  days must have elapsed from infusion of last dose of antibody, and toxicity related to prior antibody therapy must be recovered to Grade  $\leq 1$ .
- d. Corticosteroids: See [Section 4.2.2.1](#). If used to modify immune adverse events related to prior therapy,  $\geq 14$  days must have elapsed since last dose of corticosteroid.
- e. Hematopoietic growth factors:  $\geq 14$  days after the last dose of a long-acting growth factor (e.g. pegfilgrastim) or 7 days for short-acting growth factor. For growth factors that have known adverse events occurring beyond 7 days after administration, this period must be

extended beyond the time during which adverse events are known to occur. The duration of this interval must be discussed with the study chair and the study-assigned Research Coordinator.

- f. Interleukins, Interferons and Cytokines (other than hematopoietic growth factors):  $\geq 21$  days after the completion of interleukins, interferon or cytokines (other than hematopoietic growth factors)
- g. Stem cell Infusions (with or without TBI):
  - Allogeneic (non-autologous) bone marrow or stem cell transplant, or any stem cell infusion including DLI or boost infusion:  $\geq 84$  days after infusion and no evidence of GVHD.
  - Autologous stem cell infusion including boost infusion:  $\geq 42$  days.
- h. Cellular Therapy:  $\geq 42$  days after the completion of any type of cellular therapy (e.g. modified T cells, NK cells, dendritic cells, etc.)
- i. XRT/External Beam Irradiation including Protons:  $\geq 14$  days after local XRT;  $\geq 150$  days after TBI, craniospinal XRT or if radiation to  $\geq 50\%$  of the pelvis;  $\geq 42$  days if other substantial BM radiation.

Note: Radiation may not be delivered to “measurable disease” tumor site(s) being used to follow response to subprotocol treatment.

- j. Radiopharmaceutical therapy (e.g., radiolabeled antibody, 131I-MIBG):  $\geq 42$  days after systemically administered radiopharmaceutical therapy.
- k. Patients must not have received prior exposure to other NTRK inhibitors including but not limited to LOXO-101 (larotrectinib), entrectinib (RXDX-101), DS6051, PLX7486.

#### 4.1.6 Organ Function Requirements

##### 4.1.6.1 Adequate Bone Marrow Function Defined as:

- a. For patients with solid tumors without known bone marrow involvement:
  - Peripheral absolute neutrophil count (ANC)  $\geq 1000/\text{mm}^3$
  - Platelet count  $\geq 100,000/\text{mm}^3$  (transfusion independent, defined as not receiving platelet transfusions for at least 7 days prior to enrollment)
- b. Patients with known bone marrow metastatic disease will be eligible for study provided they meet the blood counts in 4.1.6.1.a (may receive transfusions provided they are not known to be refractory to red cell or platelet transfusions). These patients will not be evaluable for hematologic toxicity.

## 4.1.6.2 Adequate Renal Function Defined as:

- Creatinine clearance or radioisotope GFR  $\geq 70\text{ml/min}/1.73\text{ m}^2$  or
- A serum creatinine based on age/gender as follows:

Age	Maximum Serum Creatinine (mg/dL)	
	Male	Female
1 to < 2 years	0.6	0.6
2 to < 6 years	0.8	0.8
6 to < 10 years	1	1
10 to < 13 years	1.2	1.2
13 to < 16 years	1.5	1.4
$\geq 16$ years	1.7	1.4

The threshold creatinine values in this Table were derived from the Schwartz formula for estimating GFR utilizing child length and stature data published by the CDC.

## 4.1.6.3 Adequate Liver Function Defined as:

- Bilirubin (sum of conjugated + unconjugated)  $\leq 1.5 \times$  upper limit of normal (ULN) for age
- SGPT (ALT)  $\leq 135$  U/L. (For the purpose of this study, the ULN for SGPT is 45 U/L).
- Serum albumin  $\geq 2$  g/dL.

## 4.1.6.4 Adequate Neurologic Function Defined as:

- Patients with seizure disorder may be enrolled if on anticonvulsants and well controlled.
- Nervous system disorders (CTCAE v5.0) resulting from prior therapy must be  $\leq$  Grade 2, with the exception of decreased tendon reflex (DTR). Any grade of DTR is eligible.

4.1.7 Informed Consent: All patients and/or their parents or legally authorized representatives must sign a written informed consent. Assent, when appropriate, will be obtained according to institutional guidelines.4.2 **Exclusion Criteria**4.2.1 Pregnancy or Breast-Feeding

Pregnant or breast-feeding women will not be entered on this study due to risks of fetal and teratogenic adverse events as seen in animal/human studies. Pregnancy tests must be obtained in girls who are post-menarchal. Males or females of reproductive potential may not participate unless they have agreed to use an effective contraceptive method for the duration of study treatment.

4.2.2 Concomitant Medications4.2.2.1 Corticosteroids: Patients receiving corticosteroids who have not been on a stable or decreasing dose of corticosteroid for at least 7 days prior to enrollment are not eligible. If used to modify immune adverse events related to prior therapy,  $\geq 14$  days must have elapsed since last dose of

corticosteroid (See Section [4.1.5.1.d](#)).

4.2.2.2 Investigational Drugs: Patients who are currently receiving another investigational drug are not eligible.

4.2.2.3 Anti-cancer Agents: Patients who are currently receiving other anti-cancer agents are not eligible.

4.2.2.4 Anti-GVHD agents post-transplant:

Patients who are receiving cyclosporine, tacrolimus or other agents to prevent graft-versus-host disease (GVHD) post bone marrow transplant are not eligible for this trial.

4.2.2.5 CYP3A4 Agents: Patients who are currently receiving drugs that are strong inducers or inhibitors of CYP3A4 are not eligible. Strong inducers or inhibitors of CYP3A4 should be avoided from 14 days prior to enrollment to the end of the study. See [Appendix II](#) for a list of agents. Note: CYP3A4 inducing anti-epileptic drugs and dexamethasone for CNS tumors or metastases, on a stable dose, are allowed.

4.2.3 Patients who have received prior therapy with a specific inhibitor of TRK (including but not limited to entrectinib (RXDX-101), DS-6051b, and PLX7486) are not eligible.

4.2.4 Infection: Patients who have an uncontrolled infection are not eligible.

4.2.5 Patients who have received a prior solid organ transplantation are not eligible.

4.2.6 Patients who in the opinion of the investigator may not be able to comply with the safety monitoring requirements of the study are not eligible.

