### 7.5 Concomitant Medications

7.5.1 CYP3A4/5 inhibitors or inducers: Strong CYP3A4/5 inhibitors or inducers are prohibited from 14 days prior to enrollment to the end of the study (See [Appendix II](#) for list of agents). Avoid grapefruit or grapefruit juice as these may also increase plasma concentrations of larotrectinib.

Note: CYP3A4 inducing anti-epileptic drugs and dexamethasone for CNS tumors or metastases, on a stable dose, are allowed. Use caution in patients who are taking concomitant medications that are substrates of CYP3A4.

7.5.2 If feasible, avoid concomitant treatment with strong p-glycoprotein (P-gp) or breast cancer resistance protein (BCRP) inhibitors and strong P-gp inducers.

7.5.3 Use with caution in patients who are taking concomitant medications that are sensitive or narrow therapeutic range substrates of CYP3A4 (see [Appendix II](#)).

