#### 9.1.7 Potential Drug Interactions

Larotrectinib is a substrate of cytochrome P450 (CYP) 3A, P-glycoprotein (P-gp) and breast cancer resistance protein (BCRP). Co-administration of larotrectinib with strong CYP3A inhibitors, P-gp and BCRP inhibitors increases larotrectinib plasma concentrations. Co-administration of larotrectinib with strong CYP3A and P-gp inducers decreases larotrectinib plasma concentrations. Avoid concomitant use of strong CYP3A inhibitors or inducers for 14 days prior to enrollment through the end of protocol therapy ([Appendix II](#)). Avoid grapefruit or grapefruit juice as these may also increase plasma concentrations of larotrectinib.

If feasible, avoid concomitant administration with strong P-gp or BCRP inhibitors and strong P-gp inducers.

Larotrectinib inhibits CYP3A weakly both in vitro and in vivo. Exercise caution with concomitant use of CYP3A substrates with narrow therapeutic range (e.g. alfentanil, cyclosporine, dihydroergotamine, ergotamine, fentanyl, pimozide, quinidine, sirolimus, or tacrolimus; [Appendix II](#)) in patients taking larotrectinib. If concomitant use of these CYP3A substrates with narrow therapeutic range is

required in patients taking larotrectinib, additional toxicity monitoring and/or dose modification of the CYP3A substrates may be required due to adverse reactions.

Antacid use does not significantly alter the pharmacokinetics of larotrectinib.

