#### 11.8 Pharmacokinetic and Correlative Studies

A descriptive analysis of pharmacokinetic (PK) parameters of LOXO-101 (larotrectinib) will be performed to define systemic exposure, drug clearance, and other pharmacokinetic parameters. The PK parameters will be summarized with simple summary statistics, including means, medians, ranges, and standard deviations (if numbers and distribution permit).

All these analyses will be descriptive and exploratory and hypotheses generating in nature.

A descriptive analysis of the exploratory aims described in [Section 1.3](#) will be performed and will be summarized with simple summary statistics. All of these analyses will be descriptive in nature.

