## APPENDIX II: CYP3A4 SUBSTRATES, INDUCERS AND INHIBITORS

This is not an inclusive list. Because the lists of these agents are constantly changing, it is important to regularly consult frequently updated medical references.

CYP3A4 substrates	Strong Inhibitors 	Moderate Inhibitors	Strong Inducers	Moderate Inducers
abemaciclib acalabrutinib  alfentanil  alprazolam  amiodarone  amlodapine aprepitant/fosaprepitant atorvastatin avanafil  axitinib bortezomib bosutinib  brexpiprazole brigatinib budesonide  buspirone  cabozantinib calcium channel blockers cisapride citalopram/escitalopram cobimetinib  colchicine  conivaptan  copanlisib crizotinib cyclosporine  dabrafenib dapsone darifenacin  darunavir  dasatinib  dexamethasone  diazepam dihydroergotamine docetaxel doxorubicin dronedarone  ebastine  eletriptan  eliglustat  eplerenone  ergotamine  erlotinib estrogens etoposide everolimus  felodipine  fentanyl 	atazanavir boceprevir clarithromycin ceritinib cobicistat danoprevir/ritonavir darunavir delavirdine elivitegravir/ritonavir grapefruit  grapefruit juice  idelalisib indinavir/ritonavir itraconazole ketoconazole lopinavir/ritonavir ombitasvi +/- dasabuvir nefazodone nelfinavir paritaprevir/ritonavir posaconazole ritonavir saquinavir telaprevir telithromycin tipranavir/ritonavir tucatinib voriconazole	aprepitant conivaptan crizotinib diltiazem dronedarone duvelisib erythromycin fedoratinib fluconazole fosamprenavir fosnetupitant grapefruit  grapefruit juice  imatinib isavuconazole lefamulin letermovir mifepristone netupitant nilotinib ribociclib verapamil	apalutamide barbiturates carbamazepine enzalutamide fosphenytoin lumacaftor/ ivacaftor mitotane phenobarbital phenytoin primidone rifampin St. John's wort	Bosentan cenobamate dabrafenib efavirenz eslicarbazepine etravirine lorlatinib modafinil nafcillin pexidartinib rifabutin rifapentine

gefitinib				
haloperidol				
ibrutinib 				
idelalisib				
imatinib				
indinavir 				
irinotecan				
isavuconazole 				
itraconazole				
ivacaftor				
ketoconazole				
lansoprazole				
lapatinib				
lomitapide 				

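### The strong-CYP3A4 rule leaves two kinds of patient with unclear eligibility, and the PK summary mixes patients on and off strong inducers

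*Combined protocol and SAP*

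**What the plan says.** The rule on strong CYP3A4 agents stands in three sections, with a drug list in Appendix II.

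- **Section 4.2.2.5 (exclusion criterion).** "Patients who are currently receiving drugs that are strong inducers or inhibitors of CYP3A4 are not eligible". A second sentence says these drugs should be avoided from 14 days before enrollment until the study ends. A note then reads: "Note: CYP3A4 inducing anti-epileptic drugs and dexamethasone for CNS tumors or metastases, on a stable dose, are allowed".
- **Section 7.5.1 (concomitant medication).** "Strong CYP3A4/5 inhibitors or inducers are prohibited from 14 days prior to enrollment to the end of the study". It carries the same exemption in the same words.
- **Section 9.1.7 (agent information).** "Avoid concomitant use of strong CYP3A inhibitors or inducers for 14 days prior to enrollment through the end of protocol therapy". It does not repeat the exemption. It also states: "Co-administration of larotrectinib with strong CYP3A and P-gp inducers decreases larotrectinib plasma concentrations".
- **Section 4.1.6.4 (inclusion criterion).** "Patients with seizure disorder may be enrolled if on anticonvulsants and well controlled".
- **Appendix II.** The strong-inducer column includes carbamazepine, fosphenytoin and the run "phenobarbital phenytoin primidone rifampin". None of the anti-epileptics is marked as exempt.
- **Section 11.8 (PK analysis).** "The PK parameters will be summarized with simple summary statistics, including means, medians, ranges, and standard deviations (if numbers and distribution permit"). No split by inducer use is planned.

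Section 4.0 requires the eligibility criteria to be applied as written, with no waivers.

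**The concern.** Two things are at stake, and they are independent of each other.

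The first is eligibility. A rule that cannot be waived has to give one answer for each patient. Here it does not do so for a child who recently stopped a strong agent, or for a child without CNS disease who takes an inducing anti-epileptic. Sites may decide differently. Sections 11.5 and 11.6 build the response and toxicity sets from eligible treated patients, so an eligibility decision carries through to the denominator.

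The second is the PK description. Exempted patients receive the protocol dose without adjustment while taking a drug of a class that the protocol says lowers larotrectinib levels. Section 2.5.2 says that pediatric PK is not yet available, and aim 1.2.3 is to provide preliminary estimates in children. A single summary would mix two exposure groups.

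**Working it through.** **1. The rule, element by element**

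| Place | Force | Look-back | End | Anti-epileptic exemption |
|---|---|---|---|---|
| 4.2.2.5, first sentence | ineligible | none (current use only) | not stated | in the note |
| 4.2.2.5, second sentence | should be avoided | 14 days before enrollment | end of study | in the note |
| 7.5.1 | prohibited | 14 days before enrollment | end of study | same words |
| 9.1.7 | avoid | 14 days before enrollment | end of protocol therapy | not repeated |

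Every place that gives a look-back gives 14 days. The differences are the missing look-back in the first sentence, the force, the end point, and the exemption left out of 9.1.7.

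**2. Child who stopped a strong agent *d* days before enrollment.** In Section 4.0's counting example, a 7-day wait after 1 September allows enrollment on 8 September. A 14-day wait would then allow 15 September, so *d* = 1 to 13 lies inside the window. For those values:
- 4.2.2.5, first sentence: not currently receiving the drug, so not excluded.
- 4.2.2.5, second sentence: a recommendation or a washout criterion, depending on the reader.
- 7.5.1: breached.

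**3. Child with a non-CNS tumor and controlled seizures, on stable phenytoin.** Section 4.1.6.4 is met. If the CNS qualifier in the note attaches only to dexamethasone, the child is exempt. If it attaches to both drug types, the child is currently receiving an Appendix II strong inducer and is excluded. The grammar allows both readings.

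**4. End point.** The interval between the end of therapy and the end of study falls after the last dose. Section 8.3.2 samples PK only on Cycle 1 Day 1 and before dosing on Cycle 2 Day 1. The mismatch can change what counts as a deviation in follow-up. It cannot change the PK.

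**5. PK summary.** Let *m* of *n* PK patients be on a strong inducer that multiplies apparent clearance by *k*, with the off-inducer value set to 1.
- Mean clearance ratio = (*n* − *m* + *mk*)/*n*
- Mean AUC ratio = (*n* − *m* + *m*/*k*)/*n*

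The documents give none of *n*, *m* or *k*. As an assumption only, take *n* = 10, *m* = 2 and *k* from 2 to 5:
- Clearance: (8 + 2×2)/10 = 1.2 to (8 + 2×5)/10 = 1.8, which is 20% to 80% too high.
- AUC: (8 + 2×0.5)/10 = 0.90 to (8 + 2×0.2)/10 = 0.84, which is 10% to 16% too low.

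With *m* = 0 there is no bias. The direction follows from 9.1.7. The size does not.

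**6. Primary response rule.** For at least 3 responses in 20, the exact binomial gives 7.5% at a true rate of 5% and 90.9% at 25%. This reproduces the stated 90% power, and the attained alpha is within the stated 10% ceiling. If two of the 20 could not respond (an assumption), the other 18 must supply the responses:

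1 − (0.75^18 + 18×0.25×0.75^17 + 153×0.25²×0.75^16) = 1 − (0.00564 + 0.03383 + 0.09584) = 86.5%.

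If those two respond at 12.5% instead, power is 88.8%. At an illustrative true rate of 50%, the chance of meeting the rule is 99.98% with 20 patients and 99.93% with 18.

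**The case against.** The case on the other side is strong against several larger claims that a reader might infer.

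- *That the start of the restriction differs between sections.* It does not. The look-back is 14 days wherever one is given, and only the current-use sentence lacks it.
- *That the exemption is contradicted.* Sections 4.2.2.5 and 7.5.1 state it identically. Section 9.1.7 is drug-interaction information. It omits the exemption but does not withdraw it. Section 4.1.6.4 creates no conflict of its own, because inclusion and exclusion criteria apply together.
- *That the inconsistent wording causes the pooling.* The pooling follows from a deliberate exemption and an analysis plan without an inducer split. It would remain after perfect alignment of the text.
- *That the efficacy result is compromised.* The documents give neither the number of inducer users nor any loss of response. Assuming no response at all is extreme: Section 2.3.3 reports about 98% TRK inhibition at peak at every adult dose level, including 50 mg once daily (peak data only), and Section 2.4.1 reports confirmed partial responses in 6 of 7 evaluable fusion patients.

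It can also be said that PK is optional, that the aim is preliminary, and that 11.8 is descriptive and already reports medians and ranges, which a few outlying patients move less than the mean. That is fair and keeps the point modest. What stands against it is that 11.8 also reports means and standard deviations, and that no planned summary shows a reader which patients were induced.

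**Conclusion.** The point holds in a limited form. Two eligibility questions have no single answer in the text: the child 1 to 13 days off a strong agent, and the child without CNS disease on an inducing anti-epileptic. The end-point mismatch and the exemption missing from 9.1.7 are lesser matters of compliance and clarity.

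Separately, if any exempted patient on a strong inducer gives PK samples, the planned means will understate exposure and overstate clearance relative to patients off inducers. The direction rests on the protocol's own statement in 9.1.7. The 20% to 80% and 10% to 16% figures are illustrations under assumed inputs, not findings.

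The documents do not support a claim that the primary decision is at risk. The sample size, alpha and the 3-of-20 rule need no change.

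**What to change.** 1. Reconcile Sections 4.2.2.5, 7.5.1 and 9.1.7 into one statement giving the look-back, the force, the end point, and the scope of the anti-epileptic exemption (all tumors, or CNS disease only). The clinical team decides the content. The other places should repeat it or refer to it.
2. In Section 11.8, summarize PK parameters separately for patients on and off Appendix II strong inducers, listing individual values where a group is too small to summarize.
3. Optionally, report a descriptive response rate by inducer use. It would inform readers and change no decision.

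The cost is a wording amendment and one extra split of the PK table. The inducer group may be very small or empty. It must also be confirmed that inducer use reaches the database: the medication diaries in Appendix III ask for other drugs taken, but the case report forms are a separate packet (Section 14.1), and a site eligibility check does not by itself show that the information is captured.
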